3.6 Pembrolizumab – a monoclonal antibody targeting PD-1

3.6.1 A brief overview of pembrolizumab

Pembrolizumab (previously named lambrolizumab and MK-3475), is a highly selective humanized monoclonal IgG4-kappa isotype antibody against PD-1 currently approved by the *Food and Drug Administration* (FDA) for the treatment of patients with advanced melanoma at a dose of 2mg/kg given every 3 weeks.⁷⁷⁻⁸⁰

3.6.2 Summary of clinical experience with pembrolizumab

The first dose-escalation phase 1 study involving patients with solid tumors showed that pembrolizumab was safe across 3 tested dose levels (1mg/kg; 3mg/kg and 10mg/kg) administered every 2 weeks; of note, the maximum tolerated dose was not reached and clinical responses were observed at all of the dose levels.⁷⁷ Subsequent studies confirmed the clinical activity of pembrolizumab. Hamid et al. initially investigated pembrolizumab at doses of 2mg/kg every 3 weeks and 10mg/kg given every 2 or 3 weeks in a melanoma-only

cohort in a non-randomized fashion in the KEYNOTE-001 trial.⁷⁸ Objective responses occurred in 38% of 135 included patients. Grade 3 or 4 adverse events occurred in only 13% of the patients. In a subsequent cohort of the same KEYNOTE-001 phase I trial,⁷⁹ 173 patients with advanced melanoma were randomized to receive pembrolizumab at 2mg/kg every 3 weeks or 10mg/mg every 3 weeks. ORR was 26% at both doses after a median follow up of 8 months, with no difference in OS between different doses (estimated OS at 1 year 58% vs 63%, 95% CI 0.68-1.75). In the expansion cohort of the same trial including a total of 411 patients, pembrolizumab resulted in objective responses in 40% untreated patients.⁸⁰

3.7 Identifying predictive biomarkers for response to immunotherapy

One major challenge to harnessing immune checkpoint inhibitors in sarcomas is identifying patients who have the highest chance of benefiting from this modality of therapy. To address this question, lessons can be extrapolated from other tumor types and applied to sarcomas. We believe the heterogeneity inherent to sarcomas makes them an ideal group of tumors to validate a prospective biomarker for response to immune activating agents.

It is unclear how best to predict which patients will benefit from immune checkpoint inhibitors. While the initial phase I trial of nivolumab suggested tumors expressing PD-L1 by immunohistochemistry (IHC) may benefit more frequently from PD-1 blockade,⁷⁵ more recent data from the combination ipilimumab plus nivolumab trial has cast doubt on the theory that PD-L1 expression is necessary for therapeutic benefit. Among patients that received combination therapy, responses were seen both in patients with PD-L1 expression (6/13) or those without PD-L1 expression (9/22.)

At the ASCO 2014 meeting, there were data presented in multiple malignancies demonstrating benefit to PD-1/PD-L1 blockade for patients regardless of their PD-L1 expression. It is known that PD-L1 expression remains a dynamic marker that can change over time and under different conditions in the microenvironment. Tumor heterogeneity can also contribute to varied PD-L1 expression.⁸¹ These data suggest that PD-L1 expression may change as a result of therapy with immune checkpoint inhibitors or that other mechanisms underlie the response to immune checkpoint blockade. There remains the need to define a better biomarker predictive of response to PD-1 blockade.

3.7.1 Tumor Neoantigens May Underlie Response to Immune Checkpoint Inhibition

Recently, a report by van Rooij et al associated a response to ipilimumab in a patient with melanoma with T cell recognition of a tumor-specific mutant protein, termed a 'neoantigen'.⁸² To do this, they performed whole exome sequencing of the melanoma tumor tissue and tumor infiltrating lymphocytes (TILs) and identified >1000 tumor-specific mutations. They then utilized NetMHC, an online predictor of Class I major histocompatibility complex (MHC)-specific affinities for specific sequences of 9-11 amino acids, to narrow the mutant sequences to 448 peptides predicted to bind with medium to high affinity to the patient's CD8+ T cells.⁸³ These peptides were screened for binding with patient TILs, and they identified 3.3% of all patient CD8+ T cells reacted with a specific mutated epitope in the ataxia-telangiectasia and Rad3-related protein (ATR) pathway, suggesting this resulted in the clinical benefit seen in this patient.

Further support for neoantigen-specific immune surveillance has come from in vivo models of sarcoma. In a murine model of chemically-induced sarcomas arising in immune-deficient *Rag2*^{-/-} mice, Matsushita et al reported that implantation into an immunocompetent murine

host resulted in “immune editing” of the tumor, and tumors with a greater neoantigen load were frequently rejected by the new host.⁸⁴ Similar results were seen in a conditional Kras-p53 knockout mouse model. Whereas the work of van Rooij et al and Matsushita et al suggests that certain key mutations predict response, DuPage et al and other authors imply that a higher overall mutational load and resulting neoantigen burden may lead to efficacy.⁸⁵ The Chan lab at MSKCC has proprietary data supporting the association between this patient-specific neoantigen analysis in melanoma with individual clinical benefit from ipilimumab and tremelimumab. Whole exome sequencing was performed on tumor tissue and matched blood samples from 64 patients with melanoma who were treated with anti-CTLA-4 blockade (ipilimumab or tremelimumab). A neoantigen signature incorporating both mutational load and patient-specific neoantigens was shown to separate patients with prolonged clinical benefit from patients with progressive disease. They then validated this signature in another set of 39 patients with melanoma who were treated with anti-CTLA-4 antibodies. In this validation set predicted neoantigens activated T cells from patients treated with ipilimumab. This work defines a genetic basis for benefit to anti-CTLA-4 blockade in melanoma and provides strong rationale for examining exomes of patients receiving other immunotherapies to similarly see if a genetic basis can be defined for response or resistance to these immunotherapies.⁹⁶

Sarcoma is an ideal tumor subtype in which to test this hypothesis prospectively. The Singer laboratory at MSKCC has shown that different histologies show markedly different amounts of genetic alteration.⁸⁶ It is perhaps not surprising that a previous pilot study of ipilimumab in synovial sarcomas, a translocation-positive, genetically “simpler” tumor, produced no clinical responses.⁸⁷ There are currently no published whole exome mutation studies in sarcoma, which underscores how important this research will be to the sarcoma community.

3.8 Summary statement

Hence, there is strong rationale supporting the concept that, besides the antineoplastic effects of direct oncolysis, immune stimulation induced by GM-CSF and increased local antigen release induced by the oncolytic immunotherapy talimogene laherparepvec combined with immune checkpoint blockade using the anti-PD1 agent pembrolizumab could result in synergistic antitumoral antigen-specific activity in patients with metastatic and/or locally advanced sarcomas. The safety of this combination therapy has been explored in a phase Ib study in the setting of patients with treatment naïve, unresectable stage IIIB/IV melanoma. Ultimately, this study conveyed that the combination therapy is safe and well tolerated at full dose.⁹¹ Therefore, it is reasonable to now explore the efficacy of this combination therapy in a phase II study in patients with advanced/metastatic sarcoma.

4.0 OVERVIEW OF STUDY DESIGN/INTERVENTION

4.1 Design

This is a single-center, single-arm phase II clinical trial with additional cohorts to evaluate efficacy, as assessed by response rate, of the oncolytic herpes virus talimogene laherparepvec given in combination with the anti-PD1 monoclonal antibody pembrolizumab for patients with metastatic and/or locally advanced sarcomas.

Patients will initiate treatment with talimogene laherparepvec given intralesionally and pembrolizumab. Talimogene laherparepvec treatment will be given at Day 1 Week 1, and every 3 weeks thereafter. (Table 1). Pembrolizumab will be given at Day 1 week 1 and every

3 weeks thereafter (Table 1). Patients will be reassessed at week 8 and every 8 weeks thereafter.

Patients will be evaluated radiographically at baseline, week 8 (+/- 7 days) and every 8 weeks (+/- 7 days) subsequently until week 56 and then every 12 weeks thereafter or as per the discretion of the treating investigator. Response will be assessed using RECIST v1.1 (primary response assessment) and immune-related response criteria (irRECIST) (secondary response assessment).

The study will be sequentially monitored for pre-defined treatment-related toxicity events based on an early stopping rule as detailed in section 11. All study participants where feasible will undergo mandatory tumor biopsies, at baseline and week 8, of a distant site of disease. A site not intended to be injected is preferred for biopsy where feasible. Optional biopsies at progression will be offered. Serial blood samples will be obtained at baseline, during, and after treatment. Talimogene laherparepvec and pembrolizumab dosing should continue provided that the subject has no evidence of confirmed PD within 8 weeks of initial PD per RECIST, has no clear clinical deterioration and is able to tolerate the treatment. Treatment beyond progression will be allowed as long as patient is clinically benefitting, is tolerating the drug well and continues to meet all study treatment criteria.

Subjects with a CR or complete disappearance of the injectable lesion may stop intralesional injections of talimogene laherparepvec, but treatment with pembrolizumab will be continued for a maximum of 35 cycles of study therapy, unless one of the criteria for treatment discontinuation is met. Therapy will be discontinued due to confirmed progression of disease or clinical progression, disappearance of injectable lesions (talimogene laherparepvec only), intercurrent illness that prevents further administration of treatment, intolerance of study treatment or 24 months of treatment. Patients who discontinue study therapy after a maximum of 35 cycles of study therapy will be allowed to resume study therapy for an additional 17 cycles in the setting of progression of disease off study therapy. Safety data will be collected for up to 30 days following the last dose of the study drugs.

Study personnel will attempt to collect survival status for all patients who have confirmed disease progression after the end-of-study visit every 12 weeks (\pm 14 days) via telephone, email, or another method for up to 12 months after the end of treatment.

Patients who complete the study with a PR or CR per RECIST criteria will be followed every 12 weeks (\pm 14 days) until confirmed disease progression with the following assessments:

- Standard imaging including CT chest (with or without contrast), CT abdomen/pelvis (with contrast where renal function permits) and/or MRI abdomen/pelvis (with and without contrast) in addition to imaging of the affected area if deemed necessary by the study investigator
- Routine laboratory tests including CBC with differential, comprehensive serum chemistry panel (including glucose, blood urea nitrogen, creatinine, sodium, potassium, chloride, bicarbonate, calcium, total protein, albumin, serum bilirubin, alkaline phosphatase, ALT, and AST) and TSH
- MD visit (physical examination)

Following enrolment of the first 20 patients on this study additional cohorts will open. In the initial 20 patients enrolled on this study, the ORR overall was 35% and the ORR at 24 weeks was 30%. Objective response was observed in 5 histological subtypes including UPS, myxofibrosarcoma, cutaneous angiosarcoma, epithelioid sarcoma and undifferentiated sarcoma not otherwise specified. The additional cohorts will include a total of 40 patients and will be divided into 4 cohorts. Thirty patients with inoperable, locally advanced/metastatic sarcoma will be enrolled onto one of 3 cohorts based on sarcoma-specific subtype [i) UPS/myxofibrosarcoma, ii) epithelioid sarcoma, iii) cutaneous angiosarcoma]. Each cohort will enroll 10 patients. Patients with inoperable, locally advanced/metastatic sarcoma will be treated following the study design as highlighted above.

In the metastatic/locally advanced cohort, patients who achieve a CR or complete disappearance of the injectable lesion may stop intralesional injections of talimogene laherparepvec, but treatment with pembrolizumab will be continued. Study therapy may continue for a total of 35 cycles in the absence of confirmed progression of disease or clinical progression, disappearance of injectable lesions (talimogene laherparepvec only), intercurrent illness that prevents further administration of treatment, or intolerance of study treatment. Patients who discontinue study therapy after a maximum of 35 cycles of study therapy will be allowed to resume study therapy for an additional 17 cycles in the setting of progression of disease off study therapy. In the neoadjuvant setting, TVEC and pembrolizumab will continue for up to 8 cycles prior to surgical resection. On completion of surgery pembrolizumab alone will continue as tolerated for a total of 17 cycles (neoadjuvant and adjuvant therapy). Safety data will be collected for up to 30 days following surgical resection.

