All patients enrolled in this study will undergo biopsies at baseline and week 8 where feasible. Optional biopsies at progression will be offered. Biopsies will be done of both the lesion injected with talimogene laherparepvec and one additional target lesion, if technically feasible. Serial blood samples will be obtained at baseline, during, and after treatment. The trial schema is outlined below (**Figure 1**).

Exploratory objectives include:

- I. To investigate the rate of seroconversion in patients HSV seronegative at baseline after initial intralesional infusion of talimogene laherparepvec
- II. To evaluate associations between selected biomarkers measured in serial peripheral blood and with clinical efficacy, including immunophenotyping and Functional Analyses, evaluation of serum levels of chemokines, cytokines and other immune mediators, and characterization of T-cell receptor clonality in peripheral blood.
- III. To assess the potential effect of talimogene laherparepvec cell lysis and pembrolizumab on selected biomarker expression measured in pre- and post-treatment tumor tissue and the association between these biomarkers and with clinical outcome, including characterization of PD-1/PD-L1 expression, tumor infiltrating lymphocytes (TILs) and tumor antigens, gene expression profiling, and characterization of T-cell receptor clonality in tumor-infiltrating lymphocytes (TIL).
- IV. To evaluate the association between baseline tumor mutational burden and neoantigen production with clinical efficacy of the study therapy.

Figure 1A. Trial overview.

Additional Cohorts:

Following enrollment of the first 20 patients on this study additional cohorts will open. The additional cohorts will evaluate the efficacy and safety of T-VEC in combination with pembrolizumab in an additional 40 patients. The additional cohorts will enrich for sarcoma histological subtypes where the combination study therapy demonstrated activity in the initial 20 patients enrolled on the study including cutaneous angiosarcoma, epithelioid sarcoma, undifferentiated pleomorphic sarcoma and myxofibrosarcoma. The additional cohorts will consist of 3 cohorts of 10 patients. A metastatic/inoperable locally advanced sarcoma group (n=30) will consist of 3 cohorts of 10 patients each, based on histological subtype including epithelioid sarcoma (n=10), cutaneous angiosarcoma (n=10) and UPS/MFS (n=10)

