14.0 BIOSTATISTICS

14.1 Primary and Secondary Endpoints Statistical Considerations

The primary objective is to evaluate the efficacy, as assessed by the best objective response rate (complete response + partial response) at 24 weeks by RECIST 1.1 (primary endpoint; Phase II). The study will use a one stage design based on the exact binomial test. A 5% response rate will be considered not promising,^{94,95} a 30% response rate will be considered promising. There will be a maximum accrual of 20 patients to this study, with early stopping rules for predefined treatment-related toxicities. . It will be concluded that the true response rate is $> 5\%$ if there are 3 or more patients with an objective response among 20 patients. The design has a type I error rate of 0.08 and a type II error rate of 0.04. This design provides 96% probability of a positive result if the true response rate is at least 30%, and a 92% probability of a negative result if the true response rate is 5% or lower.

The patient population in this study represents patients with locally advanced/metastatic sarcoma that have received at least one line of previous therapy. The references supporting the 5% null rate include the PALETTE, double-blind, randomized placebo-controlled trial⁹⁴ and a study looking at the efficacy of eribulin in patients with advanced

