The number of patients who experience pre-specified treatment-related toxicity events detailed as per section 11.1.1, that result in the discontinuation of the study drug(s) or delay of their administration ≥ 9 weeks from the planned date of study drug(s) administration, will be recorded. Early stopping rules will be defined such that a 10% rate of occurrence of the above drug-related toxicities is acceptable, whereas a 30% rate would be unacceptable. The study will be continuously monitored for drug-related toxicity events that result in the discontinuation of the study drug(s) or delay of their administration ≥ 9 weeks from the planned date of study drug(s) administration. Early stopping rules are defined as observing such events in 2/4, 3/8, 4/14 or 5/20 patients. The probability of stopping under this rule is approximately 10% if the true treatment related toxicity event rate (that results in treatment discontinuation or delay in treatment administration ≥ 9 weeks) is 10%, and is approximately 79% if the true treatment related toxicity event rate (that results in treatment discontinuation or delay in treatment administration ≥ 9 weeks) is 30%. Enrollment will not pause, treatment

related toxicity events will be continuously monitored and the study terminated immediately if the pre-defined early-stopping rule boundary is crossed.

2. Toxicity

Adverse events will be graded according to the NCI CTCAE v4.03, presented on an individual basis and summarized using descriptive statistics.

3. Survival

Progression free survival (PFS) rate at 24 weeks, median PFS, overall survival (OS) Overall and progression-free survival intervals will be estimated using Kaplan-Meier methodology

4. Best Objective Response by irRECIST

Best objective response rate (complete response + partial response) at 24 weeks by immune-related Response Evaluation Criteria in Solid Tumors (irRECIST), of talimogene laherparepvec in combination with pembrolizumab in patients with metastatic and/or locally advanced sarcoma.

Descriptive statistics will be provided for demographics, safety, efficacy, and biomarkers as appropriate. Patients who have not experienced the event of interest by the end of the study will be censored at the time of the last follow-up.

Due to the small sample size, the correlative studies using tumor biopsies will be exploratory and hypothesis generating in nature.

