In relation to the design of the additional locally advanced/metastatic cohorts, there will be 3 histology specific groups: i) cutaneous angiosarcoma, ii) epithelioid sarcoma, and iii) undifferentiated pleomorphic sarcoma/myxofibrosarcoma. These sarcoma subtypes reflect the subtypes where clinical activity was demonstrated in the phase II study to date.

We expect to accrue approximately 1-2 patients each month and hence expect to finish enrollment in 15-30 months.

Secondary endpoints

1. Safety

Patients evaluable for safety analysis will include all patients who have received at least one dose of T-VEC and pembrolizumab. Adverse events will be graded according to the NCI CTCAE v4.03, presented on an individual basis and summarized using descriptive statistics.

2. Survival

Progression free survival (PFS) rate at 24 weeks, median PFS, overall survival (OS) and progression-free survival intervals will be estimated using Kaplan-Meier methodology

3. Best Objective Response Rate by irRECIST

Best objective response rate (complete response + partial response) by 24 weeks by immune-related response criteria (irRECIST), of T-VEC in combination with pembrolizumab in patients with metastatic and/or locally advanced, sarcoma.

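### Section 4.1 promises sequential toxicity monitoring of the whole study, but the only numerical boundaries end at patient 20 and none is written for the additional cohorts

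*Combined protocol and SAP*

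**What the plan says.** - **Section 4.1** introduces a single-arm phase II trial with additional cohorts and then states: "The study will be sequentially monitored for pre-defined treatment-related toxicity events based on an early stopping rule as detailed in section 11". The sentence is not limited to the first 20 patients.
- **Section 11.1.1** defines the treatment-related toxicity events (related events that lead to discontinuation or a long dosing delay) and treats them as evaluable over the whole study period. It contains no boundary.
- **Section 14.1**, under the feasibility endpoint, holds the boundaries: "Early stopping rules are defined as observing such events in 2/4, 3/8, 4/14 or 5/20 patients". The design rates are that "a 10% rate of occurrence of the above drug-related toxicities is acceptable, whereas a 30% rate would be unacceptable". The rule is tied to the initial sample size: "There will be a maximum accrual of 20 patients to this study, with early stopping rules for predefined treatment-related toxicities".
- **The protocol summary**, under Additional Cohorts, says: "The additional cohorts will evaluate the efficacy and safety of T-VEC in combination with pembrolizumab in an additional 40 patients". Both the summary and section 4.1 itemise only 30 of them (three histology cohorts of 10). These cohorts open after the first 20 are enrolled, and section 4.1 says the patients are treated under the design already described.
- **Section 14.1, additional cohorts, Safety** gives one analysis: "Adverse events will be graded according to the NCI CTCAE v4.03, presented on an individual basis and summarized using descriptive statistics". It sets no boundary and no acceptable or unacceptable rate, and does not say that the first rule continues or restarts.
- **Section 2.0** lists feasibility without early termination for toxicity as a secondary objective for the first cohort. The additional-cohort objectives omit it.

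**The concern.** The promise in section 4.1 covers the study; the rule that would carry it out covers 20 patients. With 30 additional patients, 30 of 50 (60%) fall outside any boundary; with 40, it is 40 of 60 (67%). Their toxicity events are still defined and counted, but the plan gives nothing to compare the count with. At the 30% rate the protocol itself calls unacceptable, 30 × 0.30 = 9 events would be expected among 30 additional patients (12 among 40) without a pre-specified trigger. Someone following the plan literally cannot tell whether the monitoring ended at patient 20, continues or restarts. The cross-reference to section 11 does not help, because the boundaries are not there.

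**Working it through.** **Inputs.** Boundaries 2/4, 3/8, 4/14, 5/20, design rates 10% and 30%, and stated stopping probabilities of about 10% and 79% (section 14.1, feasibility); 30 itemised additional patients (section 4.1); accrual of 1 to 2 patients a month (section 14.1, additional cohorts).

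**Method.** Exact binomial recursion. Let f(k) be the probability of not having stopped and having k events at a boundary. Moving on by m patients, f_new(k) = Σ_i f(i) · C(m, k−i) · p^(k−i) · (1−p)^(m−k+i). The probability of stopping at a boundary of r events is the sum of f_new(k) over k ≥ r; those paths are then removed. Counts are cumulative, so continuous monitoring gives the same total.

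First boundary, two or more events in 4:
- p = 0.10: 1 − 0.9^4 − 4(0.1)(0.9^3) = 1 − 0.6561 − 0.2916 = 0.0523
- p = 0.30: 1 − 0.7^4 − 4(0.3)(0.7^3) = 1 − 0.2401 − 0.4116 = 0.3483

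| Boundary | Stop here, p = 0.10 | Stop here, p = 0.30 |
|---|---|---|
| 2/4 | 0.0523 | 0.3483 |
| 3/8 | 0.0177 | 0.1635 |
| 4/14 | 0.0200 | 0.1897 |
| 5/20 | 0.0140 | 0.1142 |
| **Total to 20** | **0.1040** | **0.8156** |
| 6/26 (illustrative) | 0.0098 | 0.0682 |
| 7/30 (illustrative) | 0.0027 | 0.0216 |
| **Total to 30** | **0.1165** | **0.9054** |

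**The plan's own figures.** The four boundaries give 10.4% and 81.6%, against a stated 10% and 79%. If a crossing at the 20th patient is not counted as a stop (fifth event by patient 19), the results are 9.9% and 78.9%, which match both. This difference does not affect the point.

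**What passing the first-20 rule tells us.** The probability of passing is 1 − 0.816 = 18.4% at a 30% rate and 1 − 0.104 = 89.6% at 10%. The ratio 89.6/18.4 is about 4.9 in favour of 10%. That is real evidence, but a 30% rate still passes nearly one time in five.

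**As written, beyond patient 20.** No boundary exists, so the probability of stopping by a pre-specified rule is 0 at any true rate.

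**Illustration for the additional patients.** Start a fresh count on the 30 additional patients, pooled, and use the full sequence in the table. It stops with probability 0.1165 at 10%, 0.5665 at 20% and 0.9054 at 30%. At 30%, the mean number treated is 11.8 if every outcome is known before the next patient enrols. That is a best case: a delay of more than 9 weeks takes about two months to become an event, during which 2 to 4 more patients enrol at 1 to 2 a month.

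**Why pooled.** Restarted within each cohort of 10, only 2/4 and 3/8 can apply. They stop a cohort with probability 0.0523 + 0.0177 = 7.0% at 10%, but only 0.3483 + 0.1635 = 51.2% at 30%.

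**The case against.** The strongest reply is that the limit was intended. The rule serves the feasibility endpoint of the first 20, and the additional-cohort objectives drop feasibility and keep descriptive safety. Relaxing a formal rule for expansion cohorts after a monitored first stage is a defensible design. On that reading the defect is only that the sentence in section 4.1 was not limited to the first 20. This is possible, but the documents never say so. The whole-study wording in section 4.1, the whole-period event definition in section 11.1.1 and the statement that additional patients follow the design already described all point the other way. Either way the sections have to be reconciled.

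A reader might also infer that the additional patients have no safety oversight, or that a 30% rate could run through all of them without any action. The documents do not support that. DSMC review runs for the life of the study (section 16.2), SAE reporting continues (section 17.2), and patient-level withholding and discontinuation criteria apply (section 11.4). None of these is a numerical study-level rule, which is what section 4.1 promises, but all are routes to action.

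Nor do the first 20 patients count for little. Passing their rule favours a 10% rate over 30% by about 4.9 to 1, and section 14.1 cites a 0% rate of discontinuation for treatment-related events in the earlier trial of the combination.

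Finally, section 16.3 refers, in describing data sharing with one site, to the study as completed. If enrolment is over, new boundaries protect no one, and only the reporting remedy remains.

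**Conclusion.** The point holds in this form: sections 4.1, 11.1.1 and 14.1 do not agree, and 30 itemised additional patients (40 as stated in places) have no pre-specified numerical toxicity rule. The first-20 rule offers partial reassurance, with about an 18% chance that a 30% rate passes it. The conclusion is limited to the absence of a numerical rule; it does not extend to an absence of oversight, and the documents do not show whether the limit at 20 was deliberate.

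The 12% and 91% stopping probabilities are illustrative. They rest on the added boundaries 6/26 and 7/30, which are not in the plan, on independent outcomes with a common event rate across the pooled cohorts, and on a fresh count from the first additional patient. The figure of about 12 patients treated at a 30% rate also assumes that every event is known at once, so the true number would be higher. The change is cheap and worth making, but the gap does not invalidate the trial.

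**What to change.** 1. State in section 14.1 that toxicity-event monitoring also covers the additional locally advanced/metastatic patients, pooled across the three cohorts. Extend the boundaries to n=30 at the protocol's own 10% and 30% rates, and give the operating characteristics. The sequence ending in 6/26 and 7/30 is one example.
2. Correct section 4.1 so that it points to section 11.1.1 for the event definition and section 14.1 for the boundaries.
3. Settle whether the additional patients number 30 or 40. Reconcile the delay criterion as well: section 11.1.1 says more than 9 weeks, section 14.1 says 9 weeks or more.
4. If the rule was meant for the first 20 only, say so in section 4.1 and give the reason.
5. If enrolment is already complete, report the additional patients' event count against the 10% and 30% rates instead of adding boundaries.

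The cost is a short amendment and, with the illustrative boundaries, about a 12% chance of an unnecessary stop at a true 10% rate. That is close to the roughly 10% the protocol already accepts for the first 20.
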